We propose a pre/posttest, RCT with a 4-step (12 months per step), stepped-wedge design³ to compare effects of usual outpatient palliative care (usual care) and usual care along with either nurse-led or chaplain-led DT on patient outcomes (dignity impact, existential tasks [preparation for death, life completion], cancer prognosis awareness [peaceful awareness, treatment preferences]). We will assign 6 outpatient palliative care sites to usual care during the first-step, and randomly assign two sites per step to begin and continue DT led by either a nurse or a chaplain during each of the next 3 steps. During the usual care steps, 280 patients will complete pretest measures (patient outcomes, covariates [physical symptoms, spiritual distress], and satisfaction with palliative spiritual care services), receive usual palliative care, and complete posttest measures (patient outcomes, covariates, satisfaction). During the experimental steps as part of routine palliative care service delivery, 280 patients will complete pretest measures, receive nurse-led or chaplain-led DT, and complete posttest measures. Using mixed level analysis with site, provider (nurse, chaplain) and time (step) included in the model, we will compare the usual care and each of the DT groups for effects on dignity impact, existential tasks, and cancer prognosis awareness and explore the moderating effects of physical symptoms and spiritual distress. We will also determine the effect of usual care and DT on the patient's satisfaction with palliative spiritual care services and the report of the patient's unmet spiritual needs.

Specific Aims:

In a diverse sample of 560 elderly cancer patients, the specific aims are to:

Aim 1. Compare usual care and usual care with nurse-led or chaplain-led DT groups for effects on:

a) patient outcomes (dignity impact, existential tasks [preparation for death, life completion], cancer prognosis [peaceful awareness, treatment preferences]). We hypothesize that, controlling for pretest scores, each of the DT groups will have higher scores on the dignity impact (1° outcome) and existential tasks (2° outcome) measures than the usual care group. Also patients in each of the DT groups will report better peaceful awareness and treatment preferences more consistent with their cancer prognosis (2° outcomes) than the usual care group; and

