b) processes of delivering palliative spiritual care services (satisfaction and unmet spiritual needs; 2° outcomes). We hypothesize that each of the DT groups will show increased patient satisfaction with spiritual care services and fewer unmet spiritual needs compared to the usual care group.

Aim 2. Explore the influence of physical symptoms and spiritual distress on the dignity impact and existential tasks effects of usual palliative care and nurse-led or chaplain-led DT. We hypothesize that physical symptoms and spiritual distress will significantly affect intervention effects. This rigorous trial of DT will constitute a landmark step in gero-oncology palliative care and spiritual health services research.

Study design:

We propose a 6-site, pre/posttest, randomized, controlled 4-step, stepped-wedge design to compare the effects of usual outpatient palliative care and usual outpatient

palliative care along with nurse-led or chaplain-led DT on patient outcomes and palliative care processes. We will assign the 6 sites to usual care during the first-step period (10 months), and randomly assign 2 sites per step to begin and continue DT during each of the next 3 steps (10 months each).

Figure 1 shows the stepped-wedge study design with projected numbers of

completed patients needed per site, step period, and group (usual care, DT led by either a nurse or a chaplain). [name], a highly qualified statistician will conduct the randomization of site to steps 2-4. Each step will be 10 months long, with DT training during a 1-week period between steps. For each site/step, a quota of 50% of the participants will report low or high distress on the Personal Dignity Inventory to assure we recruit a sample with a range of problems threatening their dignity. Each patient will participate for 4-6 weeks. Over the 10 months at each step, we expect 23-24 patients to participate at each site (93-94 total patients per site).

Figure 1. Stepped-wedge design	N per step per site			Total N
Site 6	23	23	23	24 93
Site 5	23	23	23	24 93
Site 4	24	23	23	24 94
Site 3	24	23	23	24 94
Site 2	24	23	23	23 93
Site 1	24	23	23	23 93
Step	1	2	3	4
Patients/				
Step Period	142	138	138	142 560
Usual Care				280
Nurse-Led DT				140
Chaplain-Led DT				140
Step Period Duration (mo)	10	10	10	10 40

Subject identification, recruitment and consent:

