We will recruit the study sample from the population served by the six hospitals participating in this application. The sites represent the South Eastern (Emory University, UF Health Gainesville), North Midwest (Northwestern University, Rush University), South Midwest (MD. Anderson), and Western (University of California at San Francisco) areas of the U.S. The participants will be elders who are diagnosed with cancer and are receiving outpatient palliative care services at the participating sites. At UF Health, we will recruit the sample from the existing outpatient oncology palliative care services and those under development within the UF Cancer Center.

The consent process will be completed in person and in a private area at the outpatient palliative care services of the 6 sites, or at another outpatient palliative care site or other private location chosen by the potential subject to go over the details of the study and informed consent. The consent process may also be conducted by phone with the signed consent form returned by mail in a preaddressed, stamped envelope.

Procedures:

The study will be conducted in the outpatient clinic in spaces available for research or virtually via a HIPAA-compliant video-conferencing platform. The investigators will attend patient care planning meetings and introduce the study to the palliative care team members. Any member of the palliative care team will refer patients to the RA on the day the patient is seen in the palliative care clinic or via a HIPAA-compliant video-conferencing platform.

Figure 2 shows the general flow of patients through the outpatient palliative care clinics and study procedures for this study of nurse-led or chaplain-led DT over 4-6 weeks. Prior to participant recruitment, the research assistants (RA) will be trained in all study procedures. Prior to stepping up to the DT steps of the study, the nurse and chaplains at the sites scheduled to begin the DT will be trained in the DT.

Study Procedures:

- I. The RA will recruit the referred and potentially eligible patients for this study, provide and obtain informed consent, determine final eligibility, and schedule time before the next clinic visit or at a time convenient to the patient for the patient to complete the pretest tools via an audio-recorded interview documented on REDCap forms and stored on REDCap for quality control purposes.

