8. Are there particular things that you feel still need to be said to your loved ones, or things that you would want to take the time to say once again?
9. Are there words or perhaps even instructions you would like to offer your family, in order to provide help to prepare them for the future?
10. In creating this permanent record, are there other things that you would like included?

When the nurse/chaplain session(s) are completed, the nurse/chaplain will inform the RA that he/she has completed all nurse/chaplain session(s). The interview will be conducted either in person in the clinic or at a time and place convenient to the patient (e.g., home, community setting), or via a HIPAA-compliant video-conferencing platform.

III. Either in-person if the patient has a clinic visit, by telephone contact or via a HIPAA-compliant video-conferencing platform, the RA will schedule the follow-up appointment at a time and place convenient to the patient (e.g., clinic, home, community setting), and complete the audio-recorded posttest measures within 5-10 days. Upon completion of posttest measures, the RA will provide \$50 (cash or card) to the patient for time and travel expenses to complete study measures.

Sample size:

We will recruit 1500 adults with cancer diagnoses who are receiving care from the outpatient palliative care services of the six hospitals. From this sample, 560 patients will complete the study and provide data for analysis, 280 for the DT groups (140 per each of the two DT groups) and the 280 for the control groups. From UF Health, we expect to recruit 94 total patients, 23-24 per year with complete data. We will consent approximately 1,500 (250 total patients per site) for screening over the 4.5 years devoted to data collection and 120 to participate to achieve a completed sample of 94 patients per site.

Anticipated risks:

The risks of this study are primarily those regarding potential for fatigue from completing the questionnaires and the intervention, the emotionally evocative nature of the material shared during the course of the intervention, and loss of privacy. The likelihood of these risks is low, as has been observed and documented in the many previous studies of DT cited in the Background section.

Anticipated benefits:

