Aim 1. Linear mixed effects models will be used to compare the effects of usual palliative care with usual palliative care with nurse-led and chaplain-led DT groups on (a) patient outcomes and (b) processes of delivering palliative spiritual care services. Random effects terms will be used to model the variations between sites. A main challenge of data analysis of a stepped-wedge design is the modeling of potential time trends. We plan to treat time as a continuous variable and utilize smoothing splines to model potential time trends. Smoothing splines is a nonparametric method that allows flexibility to model different time trends without overfitting by enforcing a smoothness constraint. Likelihood ratio tests will be used to determine the statistical significance of the intervention effect on various outcome measures. We hypothesize that, controlling for pretest scores, patients in both nurse-led and chaplain-led DT groups will have higher dignity impact scores, higher preparation for death and life completion scores, better peaceful awareness, and treatment preferences more consistent with their cancer prognosis than the usual care groups. We also expect the patients in the DT groups to be more satisfied with the palliative care and have fewer unmet spiritual needs than the usual care groups. We do not expect significant difference between nurse-led and chaplain-led DT interventions. Note that, this does not necessarily mean that the two interventions are equally effective. We do not seek to test the equivalence of the two intervention arms. At this point, it is premature to speculate on their relative efficacy. We expect most patients in this study to have metastatic cancer. If a sizable portion of our sample has non-metastatic cancer, we will explore if they respond to DT differently than those with metastatic disease.

Aim 2. The effect of physical symptoms and spiritual distress on the dignity impact and existential tasks will be modeled nonparametrically using smoothing splines. Our models will include both main effect for physical symptoms and spiritual distress and their interactions with the intervention. This analysis will provide insight on the type of patients most in need of and most likely to benefit from the DT intervention. Likelihood ratio tests will be used to determine the significance of the interaction. We hypothesize that patients' levels of spiritual distress and physical symptom scores will moderate the intervention effect.

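### Aim 1 models calendar time but not time on DT, so if the DT effect changes with provider experience the estimate is not the patient-average effect

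*Combined protocol and SAP*

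**What the plan says.** The design section has six sites on usual care in step 1 and will then "randomly assign 2 sites per step to begin and continue DT during each of the next 3 steps". The Background and Purpose adds that DT is "randomly assign two sites per step to begin and continue DT led by either a nurse or a chaplain" in the same schedule. Sites that cross first therefore deliver DT for three steps and sites that cross last for one. Under Procedures, "the nurse and chaplains at the sites scheduled to begin the DT will be trained in the DT" before they move to DT, and the design section places that training in a one-week gap between steps.

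For Aim 1, the Data analysis section says "Linear mixed effects models will be used to compare the effects of usual palliative care with usual palliative care with nurse-led and chaplain-led DT groups", with random site effects, a smoothing spline for continuous calendar time and adjustment for pretest. It then says "Likelihood ratio tests will be used to determine the statistical significance of the intervention effect on various outcome measures". The Background and Purpose names the model terms as site, provider type and step.

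Neither place mentions time since crossover, provider learning or a sensitivity analysis for them. The Aim 2 interactions concern physical symptoms and spiritual distress. The plan never uses the word constant, but one constant DT effect per provider type follows from the terms it lists.

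**The concern.** In a stepped-wedge trial, sites already on DT help to estimate the time trend against which later crossovers are judged. In step 4 every site is on DT, so sites in their third DT step act partly as controls for sites in their first. That does no harm if the DT effect is the same at every stage. If it is not, the single estimate mixes stages in proportions unlike the patient mix, and a late stage can enter with a negative sign. The spline does not help, because it describes secular trend and not time on DT.

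A change in effect is plausible on the protocol's own facts. It says DT has not been studied with chaplains delivering it, staff are trained just before crossover, and the earliest sites then deliver it for up to 3 × 10 = 30 months. At stake is whether the reported figure can be read as the average benefit to patients who received DT.

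**Working it through.** **Plan's figures.** Figure 1 has 23 or 24 completers per site and step. The step totals are 142 + 138 + 138 + 142 = 560. If sites 1-2 cross at step 2, 3-4 at step 3 and 5-6 at step 4, DT cells sum to 138 + 94 + 48 = 280, which matches "560 patients will complete the study and provide data for analysis, 280 for the DT groups". By step on DT:

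- first: 46 + 46 + 48 = 140 (50%)
- second: 46 + 48 = 94 (34%)
- third: 46 (16%)

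**Assumptions.** The documents give no ICC, SD or effect size. I take total SD 1 and an ICC ρ from 0 to 0.2, meaning between-site variance left after pretest adjustment. The main calculation pools nurse-led and chaplain-led DT and uses categorical step.

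**Method.** Generalised least squares on the 24 site-step means: cell variance ρ + (1 - ρ)/n, covariance ρ within a site. The estimator is (D'V⁻¹D)⁻¹D'V⁻¹y, where D holds one DT indicator and four step indicators. Summing the DT row over cells at each step on DT gives weights w₁, w₂, w₃, which add to 1. The expected estimate is w₁δ₁ + w₂δ₂ + w₃δ₃, where δ is the effect in each step on DT.

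| ICC | first | second | third |
|---|---|---|---|
| 0 | 0.75 | 0.25 | 0.00 |
| 0.01 | 0.92 | 0.19 | -0.11 |
| 0.05 | 1.09 | 0.14 | -0.23 |
| 0.2 | 1.17 | 0.11 | -0.28 |
| patient share | 0.50 | 0.34 | 0.16 |

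**Illustrative effects in SD.**

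- Steep growth 0.1/0.3/0.5. Patient average (140×0.1 + 94×0.3 + 46×0.5)/280 = 65.2/280 = 0.23. Model at ICC 0: 0.075 + 0.075 + 0 = 0.15. At ICC 0.05: 0.109 + 0.042 - 0.115 = 0.04.
- Mild growth 0.30/0.35/0.40. Average 93.3/280 = 0.33. Model: 0.225 + 0.0875 = 0.31 at ICC 0; 0.327 + 0.049 - 0.092 = 0.28 at ICC 0.05.
- Waning 0.5/0.3/0.1. Average 102.8/280 = 0.37. Model: 0.375 + 0.075 = 0.45 at ICC 0; 0.545 + 0.042 - 0.023 = 0.56 at ICC 0.05.

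**Closer to the planned model.** With patient-level continuous time and a cubic smoothing spline at four smoothing levels, the third-step weight is about +0.01 to +0.02 at ICC 0, -0.07 to -0.09 at 0.01 and -0.17 to -0.20 at 0.05. The direction is unchanged and the size somewhat smaller. A site-by-step random effect with half the site variance also softens it, to -0.06 at ICC 0.01 and -0.15 at 0.05 (step-level time).

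**Separate provider contrasts.** With one nurse and one chaplain site per crossover, the ICC 0.05 third-step weight for either contrast is -0.05 on its own sites and -0.17 on the other provider's sites, about -0.23 in all before rounding. Over all 3:3 assignments of provider type to sites (linear time), the total runs from -0.29 to +0.04 at ICC 0.01 and from -0.32 to -0.04 at ICC 0.05. The documents do not say how provider type falls across steps.

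**The case against.** A reader might infer that the planned model always gives negative weight to the third DT step and so will report almost no effect when DT works. The documents do not support that. The negative weight needs residual between-site variance. At ICC 0, which a six-site fit of pretest-adjusted self-reports may return, it is nil or slightly positive. A near-null result also needs an effect that starts small and grows steeply. No such curve is in the documents, and some of the plan points the other way: DT is manualised, each of the three sessions follows a set process, a co-investigator trains the team, and each patient takes part for only 4-6 weeks, so only change in the providers could drive growth. Under mild growth the shortfall is modest (0.28 to 0.31 against 0.33).

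Nor does the point invalidate the Aim 1 test. If DT has no effect at any exposure, weights that sum to 1 return zero. If the effect is constant, the estimate is unbiased.

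These limits stand. What survives is that even at ICC 0 the third step gets almost no weight although it holds 16% of DT patients, so any change in effect is misrepresented, and nothing in the plan would reveal it.

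**Conclusion.** The concern holds as one of interpretation, and of power when the effect grows. The constant-effect estimate equals the patient-average DT effect only if the effect does not change with time on DT, or changes in a way that happens to cancel. Over ICC 0 to 0.05, steep growth averaging 0.23 SD is reported as 0.15 down to 0.04, mild growth averaging 0.33 SD as 0.31 down to 0.28, and waning averaging 0.37 SD as 0.45 up to 0.56.

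These sizes rest on an assumed ICC, SD scale and set of curves, on pooled DT and on categorical step; the planned spline gives a smaller negative weight. For nurse-led and chaplain-led contrasts the size cannot be fixed until the spread of provider type over steps is known. The step length is given as 12 months in the Background and Purpose and 10 in the design section; this does not affect the weights.

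**What to change.** Keep the constant-effect model as the primary Aim 1 analysis. Pre-specify one supportive model that replaces the single DT term with separate terms for the first, second and third step since crossover. Beside the primary result, always report the three step-specific estimates and their patient-weighted average (50/34/16) with a confidence interval. Describe the primary estimate as assuming a constant effect over time on DT.

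Do not make that wording depend on a test that the two estimates agree. The variance of their difference is the difference of their variances, so its standard error at ICC 0.05 is √(0.186² - 0.150²) ≈ 0.11. Even the steep curve then gives z ≈ (0.23 - 0.04)/0.11, about 1.8, and about 1.9 at ICC 0.02. A 5% test would detect it less than half the time.

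The cost is one model and a few sentences, on data already collected, and the primary test is unchanged. The supportive average is less precise. With DT pooled its standard error exceeds the primary one by about 4% at ICC 0, 17% at ICC 0.02 (0.145 to 0.169) and 24% at ICC 0.05 (0.150 to 0.186). Precision is lower within each provider group. The third-step term rests on two sites and 46 patients and should be read with its interval.

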The MPIs ([name], [name], [name]) will evaluate the progress of the study, including periodic assessments of data quality and timeliness, participant recruitment, accrual and retention, participant risk versus benefit, and other factors that could affect study outcomes. The MPIs also monitor for scientific or therapeutic developments that may have an impact on the safety of the participants or the ethics of the study. The MPIs make recommendations to the IRB and the site directors concerning continuation or conclusion of the trial.

Data analysis:

Data management and preliminary data analysis procedures will be supervised by MPI [name] and conducted by [name], the Co-I and statistician, using statistical software R. Data will be stored in a REDCap database and will be exported to R. In the case of missing data, multiple imputations will be used to generate multiple complete datasets on which statistical inference will be performed. Missing at random assumption will be assessed and if necessary sensitivity analysis will be performed using pattern mixture methods. We will consider a p value less than .05 as statistically significant.

Descriptive statistics (ranges, frequencies, means, and standard deviations) and graphic summary (box plots, histograms, bivariate scatter plots, etc.) will be first generated for both patient covariates and outcome measures. We will check patient characteristics to see if there is notable imbalance between the three arms, as well as whether there is significant variations between sites or over time. Descriptive statistics of patient outcomes and process data will reveal patients' spiritual state, identify potential areas for improvement in nurse and chaplain service, and provide information on nurses' and chaplains' workload both in usual care and when dignity therapy is added and on family-related variables (e.g., legacy document disposition, etc.).

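### Aim 1 names the pretest score as its only patient-level covariate, so a change in who is referred when a site starts DT would enter the DT estimate; baseline covariates already collected should be pre-specified

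*Combined protocol and SAP*

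**What the plan says.** The Aim 1 paragraph of Data analysis specifies linear mixed models. For site: "Random effects terms will be used to model the variations between sites". For time: "We plan to treat time as a continuous variable and utilize smoothing splines to model potential time trends". The patient-level adjustment appears only in the hypothesis: "We hypothesize that, controlling for pretest scores, patients in both nurse-led and chaplain-led DT groups will have higher dignity impact scores". The design summary in Background and Purpose gives a matching list of terms: "Using mixed level analysis with site, provider (nurse, chaplain) and time (step) included in the model". No other patient characteristic is named for Aim 1.

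On how patients enter, Study design randomises sites to the step at which they start DT. The care a patient receives then follows from site and step (Study Procedures, item II). Under Procedures, "Any member of the palliative care team will refer patients to the RA on the day the patient is seen". The same section has nurses and chaplains trained in DT before their site crosses over. No concealment of the site's condition from referrers is described.

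Four other provisions bear on the point:
- Study design sets "a quota of 50% of the participants will report low or high distress on the Personal Dignity Inventory", per site and step. Exclusion criterion 4 applies the quota to two scales, dignity and spiritual distress.
- Background and Purpose labels physical symptoms and spiritual distress as covariates. Aim 2 enters them as main effects and as interactions with the intervention, for dignity impact and existential tasks.
- Performance status and demographics are also collected (Inclusion criteria; Data collection and management).
- Data analysis adds: "We will check patient characteristics to see if there is notable imbalance between the three arms". It states no consequence for the model.

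**The concern.** Randomising sites to steps balances the timing of DT across sites. It does not balance the patients recruited within a site before and after crossover. The people who can refer include the nurses and chaplains who have just been trained to deliver DT. That they know their site's condition is an inference, but a strong one. If they then refer somewhat fitter or less symptomatic patients, the change begins exactly when DT begins.

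A random site effect removes stable differences between sites. A smooth time curve removes gradual trends. Neither removes a within-site change that coincides with the intervention indicator. The pretest score removes only the part of the change that it reflects. The rest would be counted as an effect of DT, on the primary outcome (dignity impact) and on the secondary outcomes.

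**Working it through.** **1. The plan's own figure.** The Figure 1 rows sum to 93 + 93 + 94 + 94 + 93 + 93 = 560, and the columns to 142 + 138 + 138 + 142 = 560. Usual care comprises all sites in step 1 (142), four sites in step 2 (4 × 23 = 92) and two sites in step 3 (2 × 23 = 46): 142 + 92 + 46 = 280, whichever sites cross over when. DT has 560 − 280 = 280. The stated sample is reproduced. The documents give no SD, intracluster correlation, effect size or power, so no standard error can be derived from them. Everything below is illustrative.

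**2. Bias formula.** Let a baseline trait shift by *s* SD in DT periods, beyond what the pretest reflects, and let it have partial slope *g* on the outcome given the pretest. With site, time and pretest in the model, the bias in the DT effect is *g × s*. The two-sided rejection rate under no true effect is P(|Z + bias/SE| > 1.96).

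Assumed inputs: *s* = 0.2-0.3, *g* = 0.2-0.3, SE = 0.12-0.16 SD.
- Low end: bias 0.2 × 0.2 = 0.04; 0.04/0.16 = 0.25; rejection about 5.7%.
- High end: bias 0.3 × 0.3 = 0.09; 0.09/0.12 = 0.75; rejection about 11.6%.

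**3. Simulation of the Figure 1 layout.** Six sites, four steps, N = 560, no true DT effect, 1,500 runs per row. Fixed site and step effects stood in for the random effects and the spline, and the two DT groups were pooled. Assumed: residual SD 0.8, pretest slope 0.5, quota met exactly in every cell.

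| *g* | *s* | Pretest only: bias / SE / rejection | Plus the covariate: bias / SE / rejection |
|---|---|---|---|
| 0.2 | 0 | −0.002 / 0.134 / 4.5% | −0.002 / 0.130 / 5.1% |
| 0.2 | 0.2 | 0.036 / 0.133 / 5.5% | −0.004 / 0.130 / 4.9% |
| 0.2 | 0.3 | 0.065 / 0.133 / 7.9% | 0.005 / 0.130 / 4.7% |
| 0.3 | 0 | −0.001 / 0.138 / 4.5% | −0.001 / 0.130 / 4.7% |
| 0.3 | 0.2 | 0.052 / 0.138 / 6.5% | −0.005 / 0.130 / 4.4% |
| 0.3 | 0.3 | 0.086 / 0.138 / 10.4% | −0.002 / 0.130 / 5.4% |
| 0.3 | 0.5 | 0.159 / 0.138 / 20.3% | 0.005 / 0.131 / 5.5% |

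Monte Carlo error is about √(0.05 × 0.95/1500) = 0.6 percentage points on the rejection rate and 0.13/√1500 = 0.003 on the bias. Small differences between rows should not be read closely. The pattern agrees with *g × s*: the bias survives site and step terms and disappears once the shifted trait is in the model.

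**4. Quota stratum.** Adding it to the model with the covariate left the bias unchanged and moved the SE from 0.130 to 0.129, under 1%.

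**The case against.** Several protections are already in the plan, and most of this case stands.

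- *The quota.* Half low and half high distress in every site and step coarsely balances distress before and after crossover, if the quota is met. That is a real safeguard. It is a two-category cut, though, and does not constrain performance status, physical symptoms or age.
- *Aim 2.* Two of the covariates proposed here already enter planned models of dignity impact and existential tasks. Those models test moderation and do not supply the Aim 1 estimate. Peaceful awareness, treatment preferences, satisfaction and unmet needs have no such model.
- *Eligibility.* The requirement of a Palliative Performance Scale above 50 narrows the range of fitness somewhat.
- *The source text.* The pretest adjustment is named in a hypothesis, not in a model formula. Still, no other section names a further patient-level term for Aim 1.

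A reader might also infer more than the documents support:
- *That covariates will be picked after inspecting imbalance.* Data analysis does not say this. The fair criticism is that the check has no stated consequence.
- *That omitting the quota stratum wastes appreciable precision.* The working shows almost no loss when the quota is met.
- *That covariate adjustment would cure referral selection.* It removes measured differences only, and Data collection and management lists no measure of receptiveness to DT.

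**Conclusion.** The concern holds as a gap in the Aim 1 specification. The pretest score is the only patient-level covariate named, in a design where the condition is fixed by site and step before referral. A referral shift at crossover would pass into the DT estimate despite the site and time terms.

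It would be wrong to read this as showing that the DT estimate is biased. Nothing in the documents shows that a shift will occur, and its size cannot be derived from them. With shifts of 0.2-0.3 SD, partial slopes of 0.2-0.3 and a standard error of 0.12-0.16 SD, all assumed, the 5% error rate rises to roughly 6-12%. The simulation gave 5.5-10.4% for the same shifts and slopes. With no shift, every model stayed near 5%, so adjustment costs little if the worry proves empty. Because the simulation pooled the two DT groups, a comparison of one DT group with usual care would usually have a larger standard error, and the same bias would then inflate the error rate less.

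**What to change.** State in Data analysis that every Aim 1 model includes, besides the pretest value of the outcome where one is measured, these baseline covariates: Palliative Performance Scale, physical symptoms, spiritual distress and age. Say that the imbalance check is descriptive and does not alter this list. Add one sentence acknowledging that differences in unmeasured traits, notably receptiveness to DT, are not removed.

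The quota stratum is an optional addition that should bring little precision. It cannot be added until its definition is reconciled: Study design uses one scale and exclusion criterion 4 uses two, and patients low on one and high on the other are not addressed.

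The cost is a short addition to the text, made before outcome data are analysed. All four variables are already collected. As linear terms they use four degrees of freedom out of 560 patients, and the planned multiple imputation can cover missing values. The recruitment procedure does not change.
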